8.2 Analysis of Hemorrhage Rates

The incidence of hemorrhage, overall and by type (as defined above), will be summarized in a table similar to the one below:

Table 3. Bleeding Rates

Type	Total (N = XX)	Treated (N = XX)	Placebo (N = XX)	P-Value
Hemorrhage (Volume > 0.06 mL)	XX (%)	XX (%)	XX (%)	X.XX
(Volume > 0 mL)	XX (%)	XX (%)	XX (%)	X.XX
(Volume > 0.5 mL)	XX (%)	XX (%)	XX (%)	X.XX
(Volume > 1.8 mL)	XX (%)	XX (%)	XX (%)	X.XX
Microbleeds	XX (%)	XX (%)	XX (%)	X.XX

To assess tPA/mechanical thrombectomy-related hemorrhage rates across the two groups, all treated subjects (regardless of dose) will be compared to placebo subjects using a Pearson chi-square test. This test will assess the null hypothesis that there is no relationship between treatment group assignment and hemorrhage rates versus the alternative hypothesis that the groups differ with respect to hemorrhage rates. If any of the expected cell counts are too small to justify the use of the Pearson chi-square test, Fisher’s Exact test will be used instead.

If we fail to reject H_0 , then we will conclude that there is no significant difference between the placebo and 3K3A-APC groups. If H_0 is rejected, then we will conclude that the two groups differ with respect to hemorrhage rates – with the direction of the difference indicating which group has an increased (decreased) risk of hemorrhage. For example, if H_0 is rejected and the hemorrhage rate is lower in the 3K3A-APC group, then we will conclude that participants in the 3K3A-APC group have a significantly lower rate of hemorrhage than participants in the placebo group.

An additional analysis will compare the total hemorrhage rates among placebo subjects and subjects treated at each dose level (assuming a sufficient number of subjects were treated at that level). Again, if the assumptions of the Pearson chi-square test are not met, then Fisher’s exact test will be used instead.

All prior analyses will be repeated to compare the groups with respect to incidence of microbleeds at Day 30.

8.3 Exploratory Outcomes

A number of additional exploratory analyses are also planned, but will not be included as part of the FSR. Unless explicitly stated otherwise, the comparisons will be conducted first comparing all treated subjects (regardless of dose) versus all placebo subjects, and then comparing each dose individually. These exploratory analyses include, but are not limited to the analyses described below.

- This study will include additional bleeding outcome data of interest. While the sample size is likely too small to observe meaningful treatment effects, the data allow confirmation that outcomes in this trial resemble previously published trials. Corresponding, the following exploratory analyses will be considered:
 - Evaluating the effect of 3K3A-APC on the volume of tPA/mechanical thrombectomy related hemorrhage in the brain as determined by MRI at Day 30
 - Evaluating the effect of 3K3A-APC on the incidence of subarachnoid hemorrhage in subjects who receive mechanical thrombectomy
 - Evaluating the effect of 3K3A-APC on the incidence of hemorrhage at Day 7.
- To inform the design of any future phase II/III trial, the study will also include outcome data typically collected in all stroke trials, as well as sample collection to assess the immunogenic potential of 3K3A-APC. Correspondingly, additional exploratory analyses will include comparisons across groups for:
 - Day 7 National Institute of Health Stroke Scale (NIHSS) Scores
 - Change from Baseline NIHSS to Day 7 NIHSS
 - Day 90 Modified Rankin Scale (mRS)
 - Infarct Volume at 90 Days (MRI, or CT if unable to obtain MRI):
 - Day 90 Barthel Index (BI) Scores
 - The relationship between the 7-day NIHSS score and the 90-day mRS will be examined using a linear regression model. The degree of fit and the R-square will be determined, and the model will be used to assess the potential for using the 7-day outcome in subsequent studies.
 - Pre-Dose 1, Day 14, and Day 30 Anti-Drug Antibody Samples: The tendency of the drug to induce an immunogenic response in patients will be assessed.

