8.5.2 Secondary Objectives

Secondary Outcome #1 (PK Parameters): Based upon analysis of PK data from the Phase I study, a one-compartment IV infusion model will be used and will be parameterized in terms of the primary parameters clearance (CL) and volume of distribution (V). Secondary parameters will include C_{max} , AUC_{0-inf}, and $t_{1/2}$ – and will be calculated from the primary parameters. The actual times of the beginning and end of all 5 infusions and each blood sampling time relative to the first dose will be used in the modeling. All modeling will be done using WinNonlin.

Secondary Outcome #2 (Bleed Rates): To assess tPA/mechanical thrombectomy-related bleed rates across the two groups, all treated subjects (regardless of dose) will be compared to all placebo subjects using a Pearson chi-square test. An additional analysis will compare the bleed rates among placebo subjects and subjects treated at each dose level (assuming a sufficient number of subjects were treated at that level).

Exploratory Outcomes: (Stroke Outcome and Immunogenicity Data): To inform the design of any future Phase III trial, the following exploratory outcomes will be compared at the end of the study. Unless explicitly stated otherwise, the comparisons will be conducted first comparing all treated subjects (regardless of dose) versus all placebo subjects, and then comparing all subjects receiving the dose selected as the MTD versus all placebo subjects.

• The mean bleeding (hemorrhage and microbleeds) volume at Day 30 will be compared using a linear regression model. Median and categorical volumes (based upon quartiles) will be compared.

- Rates of subarachnoid hemorrhage in subjects who receive mechanical thrombectomy will be compared; all mechanical thrombectomy 3K3A-APC-treated subjects (regardless of dose) will be compared to all placebo subjects using a Pearson chi-square test.
- The 7-day NIHSS mean scores will be compared using a Kruskal-Wallis test.
- The change from Baseline NIHSS to 7-day NIHSS will be compared using a linear regression model, with baseline NIHSS score as a covariate.
- The 90-day mRS will be compared using a Pearson chi-square test.
- The mean infarct volume at 90 days (MRI, or CT if unable to obtain MRI) will be compared using a linear regression model. Median and categorical infarct volumes (based upon quartiles) will be compared.
- The 90-day BI will be compared using a Kruskal-Wallis test.

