NN104

Statistical Analysis Plan

RHAPSODY: Safety Evaluation of 3K3A-APC in Ischemic Stroke

[name], FAAN, FAHA
Chairman, Department of Neurology
Cedars-Sinai Medical Center
Protocol Principal Investigator

[name], MBA
Chief Operating Officer
ZZ Biotech
X01 Principal Investigator

VERSION 2.0
December 07, 2017

STATISTICAL ANALYSIS PLAN SIGNATURE PAGE

NN104

[RHAPSODY: Safety Evaluation of 3K3A-APC in Ischemic Stroke]

Protocol Principal Investigator Approval

Signature: [name] **Date:** 12/7/2017

[figure not shown]
Name: [name], FAAN, FAHA

X01 Principal Investigator Approval

[figure not shown]
Signature: [name] **Date:** 7 Dec 2017

Name: [name], MBA

NeuroNEXT Clinical Coordinating Center Approval

Signature:  12/8/2017
Name: 

NeuroNEXT Data Coordinating Center Approval

Signature:  **Date:** 12/08/2017
Name: 

SUMMARY OF CHANGES

SEPTEMBER 2017 - VERSION 1.0

- Initial version

OCTOBER 2017 - VERSION 1.1

- Modified language in section 3.2 describing outcome definition for key secondary endpoint assessing hemorrhage rates

DECEMBER 2017 - VERSION 2.0

- Modified language in sections 3.2, 6.3, and 8.2 to include revised definitions for key secondary endpoint assessing hemorrhage rates based on discussions at 10/2017 Iowa meeting and follow-up calls with NINDS to address issues with values obtained via central read. Modified language in section 10.1 to clarify specific requests for coding of certain AEs.

PREFACE

This statistical analysis plan (SAP) describes the planned analysis for the NeuroNEXT NN104 (RHAPSODY) study [National Institute of Neurological Disorders and Stroke (NINDS) grant # U01NS088312]. The planned analyses identified in this SAP are intended to support the completion of the Final Study Report (FSR) and will be included in regulatory submissions and/or future manuscripts. All interim analyses will involve only the primary study endpoint, and will be performed once each cohort has been enrolled and completed the study period for assessing dose-limiting toxicities. All final, planned analyses identified in this SAP will be performed only after the last subject has completed the full study period. Once all data have been cleaned and verified, a “locked” version of the data will be used for reporting the final study results. Key statistics and study results will be made available to the PPI and CCC following database lock and prior to completion of the final FSR.

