2. PRIMARY ENDPOINT

The primary objective of the study is to evaluate the safety of multiple ascending intravenous (IV) doses of 3K3A-APC following tPA administration in subjects who have experienced moderate to severe acute hemispheric ischemic stroke. Safety will be assessed by defining dose limiting toxicities (DLTs), which will be graded using the National Cancer Institute (NCI) Common Terminology Criteria for Adverse Events (CTCAE), Version 4.03.

DLTs will be assessed from the first dose to 48 hours following the last dose of study treatment (unless specified below), and defined as any of the following AEs that have an attribution of “related” to study treatment (possibly, probably and definitely):

- An activated partial thromboplastin time (aPTT) that reaches 2x the upper limit of normal (ULN) at 1 hour post-dose. The ULN range is defined locally by the site laboratory.
- Symptomatic intracranial hemorrhage (SICH) defined as blood present on CT or MRI brain image that is associated with clinical worsening that meets the definition of neuroworsening (4 or more point increase on the NIHSS; see section 10.3 for definition) *and* in the opinion of the investigator represents a clinically significant change that can be attributed to the hemorrhage. Subarachnoid hemorrhage that occurs in subjects who receive mechanical thrombectomy will NOT be considered a DLT, and instead will be evaluated in an exploratory analysis upon study completion.
- Findings that meet all of the following three components (Hy’s Law):
 - $\geq 3x$ ULN of alanine aminotransferase (ALT) or aspartate aminotransferase (AST)
 - Serum total bilirubin (TBL) $> 2x$ ULN, without initial findings of cholestasis [serum alkaline phosphatase (ALP) activity $> 2x$ ULN]
 - And, no other reason can be found to explain the combination of increased aminotransferase (AT) enzymes and TBL, such as viral hepatitis A, B, or C, pre-existing or acute liver disease, or another drug capable of causing the observed injury.
- Any other bleeding event classified as serious by the Investigator, or any bleeding that required the administration of more than 2 units of packed red cells over any two consecutive days.
- Any Grade 3 laboratory value that, in the opinion of the investigator, is related to study treatment.

- Any adverse event that, in the opinion of the investigator, is related to study treatment and leads to cessation of further dosing.

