10. SAFETY MONITORING

Safety will be monitored by physical examinations, vital signs, clinical laboratory tests (i.e., chemistries, hematology, coagulation studies, and urinalysis), CT and MRI, ECGs, and adverse event (AE) assessment. Safety assessments will compare the groups on the basis of all AEs, changes in laboratory and vital signs values, and results of physical examinations. AE data will be listed individually, and will be descriptively summarized by body system, preferred terms within a body system, and treatment dose.

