10.8 Safety Analyses

In addition to the determination of an MTD, additional safety assessments will involve a comparison of treatment-related AEs and SAEs across all 3K3A-APC treated subjects (regardless of dose) versus placebo. First, the percentage of subjects who experience any treatment-related AE or SAE in each group will be compared using a Fisher's exact test. If the null hypothesis is rejected, with a greater frequency observed in the 3K3A-APC group, we will conclude that 3K3A-APC was associated with a significantly greater frequency of treatment-related AEs. If the hypothesis is not rejected, we will conclude that the study does not provide sufficient evidence to conclude that 3K3A-APC was associated with a significantly greater frequency of treatment-related AEs. In addition to an overall comparison, this hypothesis will be repeated for the percentage of subjects having at least one treatment-related AE within each MedDRA system organ class (SOC). If there are significant differences between groups within any specific SOC, then additional tests will compare differences across groups for specific MedDRA preferred terms in order to further explore the cause of observed differences.

In addition to the comparison of percentages in the manner described above, the rates of treatment-related AEs in each group will be compared using the following Poisson regression model:

$$\log\left(\frac{Y_i}{T_i}\right) = \beta_0 + \beta_1 x_{1i} + \epsilon_i$$

where

- Y_i represents the number of treatment related SAEs experienced by the i^{th} subject.
- T_i represents the number of days between the date of randomization and the date of last follow-up for the i^{th} subject.
- $x_i = 1$ if i^{th} subject was randomized to one of the 3K3A-APC dose groups, and 0 if the subject was randomized to placebo group
- ϵ_i is random error for the i^{th} subject

To determine if the rate of treatment related SAEs differ across treatment group we will test the following hypothesis:

$$H_0: \beta_1 = 0 \text{ vs. } H_A: \beta_1 \neq 0$$

If the null hypothesis is rejected, the direction of β_1 will indicate the direction of the observed effect. Values of $\beta_1 > 0$ indicate an increased rate of treatment-related AEs associated with the 3K3A-APC group, while values of $\beta_1 < 0$ indicate a decreased rate of treatment-related AEs associated with the 3K3A-APC group.

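### The subarachnoid hemorrhage comparison that stands in for DLT counting in thrombectomy subjects is left out of the Final Study Report

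*SAP*

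**What the plan says.** SAP 2 defines the primary safety endpoint and makes one exception: "Subarachnoid hemorrhage that occurs in subjects who receive mechanical thrombectomy will NOT be considered a DLT, and instead will be evaluated in an exploratory analysis". Protocol 3.1.1 and 8.2.1 carry the same exception. It has no severity limit, so symptomatic SAH in a thrombectomy subject is excluded as well.

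Protocol 1.3 makes SAH in thrombectomy subjects an exploratory objective. Protocol 8.5.2 commits to the analysis: "Rates of subarachnoid hemorrhage in subjects who receive mechanical thrombectomy will be compared", using a Pearson chi-square test.

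SAP 8.3 opens with "A number of additional exploratory analyses are also planned, but will not be included as part of the FSR". Under it, among bleeding analyses put forward for consideration, stands "Evaluating the effect of 3K3A-APC on the incidence of subarachnoid hemorrhage in subjects who receive mechanical thrombectomy". The section gives no test, data source or other report for this item. By contrast, SAP 8.1 keeps the PK results out of the FSR but assigns them to a separate report.

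The general safety outputs are not excluded from the FSR. SAP 10 states: "AE data will be listed individually, and will be descriptively summarized by body system, preferred terms within a body system, and treatment dose". SAP 10.8 adds between-group tests by MedDRA organ class, with this condition for going further: "If there are significant differences between groups within any specific SOC, then additional tests will compare differences across groups". It also compares neuroworsening events, DLTs and deaths, and repeats the analyses for each dose against placebo.

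**The concern.** The exception in SAP 2 is an exchange: SAH in thrombectomy subjects does not count toward the DLT rate that sets the MTD, and a separate analysis covers it instead. The exchange works only if the separate analysis appears where the MTD is read. SAP 8.3 leaves it out of that report and weakens it from the protocol's commitment to something to be considered.

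Safety is the primary objective, and Protocol 2.3.3 describes bleeding as the dose-limiting side effect of the wild-type molecule. A reader of the FSR would see an MTD from which one bleeding type had been removed by definition. No planned table would show how often that type occurred, by arm, in the subjects to whom the exception applies.

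**Working it through.** The plan states no figure on this point, so there is none to reproduce. The check is a cross-reading.

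**Step 1. Which planned outputs could show SAH in a thrombectomy subject?**

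| Output | Where | Could SAH appear? | Limit |
|---|---|---|---|
| DLT and MTD table | SAP 7 | No | Excluded by definition |
| Adverse event listing and preferred-term summary by dose | SAP 10 | Yes, if reported as an AE or SAE; no significance gate | Not split by recanalization therapy |
| Organ-class tests | SAP 10.8 | Yes, mixed with all other events in the class | Preferred terms tested only after a significant class result |
| Neuroworsening comparison | SAP 10.3, 10.8 | Only if the definition is met | Mixed with edema, hydrocephalus and extending infarct |
| Day 30 bleeding table | SAP 3.2, 8.2 | No SAH row | Hemorrhage is defined from hematoma and petechial blood; microbleeds are separate |
| SAH comparison in thrombectomy subjects | SAP 8.3 | Yes | Outside the FSR |

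**Step 2. Does every SAH reach the adverse event outputs?** Not necessarily. Protocol 9.4.1.1 and SAP 10.1 do not capture outcome-measure results as adverse events, and Protocol 8.2.2 lists SAH incidence among the exploratory outcomes. Non-serious events are collected only through Day 7 and serious ones through Day 30. An SAH seen only on a study scan may therefore never be entered.

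**Step 3. How well does the organ-class gate stand in for a direct test?** This is an illustration, not a result from the documents.

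- Group sizes: 22 × 3 = 66 active; 115 − 66 = 49 placebo.
- Assumed: thrombectomy share m of 30% or 50%; SAH rate s among thrombectomy subjects of 30% or 15% on active and 5% on placebo; background rate q of 30% or 60% for other events in the class, independent of SAH; Fisher's exact test, two-sided 0.05. The SAP states 0.05 for the key secondary analyses, and it is carried over here.
- Thrombectomy subjects: at m = 30%, 66 × 0.3 ≈ 20 and 49 × 0.3 ≈ 15; at m = 50%, 33 and 24 (24.5 rounded down).
- Proportion with any event in the class: p = 1 − (1 − q)(1 − m·s). For m = 50%, q = 30%, SAH 30% against 5%: active 1 − 0.7 × 0.85 = 0.405; placebo 1 − 0.7 × 0.975 = 0.318.

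Power by exact enumeration:

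| m | SAH active / placebo | Direct test | Class gate, q = 30% | Class gate, q = 60% |
|---|---|---|---|---|
| 30% | 30% / 5% | 36.1% | 7.1% | 4.8% |
| 50% | 30% / 5% | 64.2% | 13.0% | 6.9% |
| 30% | 15% / 5% | 3.4% | 4.4% | 3.9% |
| 50% | 15% / 5% | 12.9% | 5.3% | 4.2% |

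For a large difference, the gate opens the preferred-term test in at most 13% of trials, against 36% to 64% for a direct test. For the smaller difference, neither has useful power. The case for the dedicated table is therefore that the counts should be visible, not that a test would settle the question.

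**The case against.** The strongest reply is that SAH is openly exploratory and its analysis has not been cancelled. SAP 2 promises an analysis at study completion, not a place in the FSR. The SAP Preface allows the planned analyses to go into regulatory submissions or manuscripts as well. Protocol 8.2.2 and SAP 8.3 both concede that the sample is small for the exploratory outcomes. The medical monitor reviews SAEs in real time, and the DSMB reviews accumulating safety data. All of this stands. It shows that SAH is neither hidden nor unmonitored, but it does not put the thrombectomy-restricted counts beside the MTD.

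A reader might infer more than the documents support:

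- **That the FSR has no information on SAH.** It does not follow. SAH reported as an AE or SAE appears in the listing and the ungated preferred-term summary by dose, enters the organ-class tests, and enters the neuroworsening comparison if it qualifies.
- **That the coding rule in SAP 10.1 erases SAH.** The rule names three terms, and SAH is not one of them. Sites are told to record the specific disease where they can discern it. A merger with cerebral hemorrhage would need a site to use a generic term.
- **That a known amount of bleeding is missing from the 10% DLT ceiling.** The documents give no thrombectomy share and no SAH rate. Much SAH would not have been a DLT even without the exception, because it would still have had to be treatment-related, fall within 48 hours of the last dose and meet one of the DLT criteria.

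**Conclusion.** The point holds in this form: SAH in thrombectomy subjects, including symptomatic SAH, leaves the DLT count in exchange for an exploratory analysis, and SAP 8.3 then makes that analysis optional in wording and omits it from the FSR, against the commitment in Protocol 8.5.2. What remains in the FSR is partial. It pools over recanalization therapy, depends on adverse event reporting, and is gated for any preferred-term test.

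The size is one missing table in the report of the primary safety objective. No count of affected events can be given. The conclusion rests on the text alone and does not need the assumed rates in the power illustration. It does not put the MTD rule in question. The change is worth making because it is nearly free and closes the gap between the exception and its stated replacement.

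**What to change.** Move the SAH comparison from SAP 8.3 to SAP 10.8 and include it in the FSR beside the DLT and MTD table. State it as planned, in line with Protocol 8.5.2.

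- **Population:** thrombectomy subjects only, in both the active and the placebo group. Say so explicitly, because Protocol 8.5.2 names the comparator simply as all placebo subjects.
- **Content:** number and percent with any SAH and with symptomatic SAH, for all 3K3A-APC, each dose and placebo, with exact 95% confidence intervals. Give Fisher's exact test as descriptive support only.
- **Symptomatic SAH:** use the existing neuroworsening definition. Protocol 9.4.1.3 confines it to the DLT observation period, so a footnote should say that this row covers that window.
- **Data source:** AE/SAE report, central read, or both. SAP 3.2 describes hemorrhage location and volume on the reader's form but no explicit SAH item, so check that the central read can supply it.

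The DLT definition and the coding rule need no change. The cost is SAP wording, confirmation of the data source, and one extra table with small cells and low power.

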9. SAMPLE SIZE CONSIDERATIONS

9.1 Primary Outcome

In order to assess the adequacy of the sample size, we conducted a simulation study to examine the ability of the study to identify the MTD under a range of assumed scenarios. The scenarios under consideration are summarized below in Table 4.

Table 4. Assumed True Toxicity Probabilities for Simulation Scenarios

Scenario	Description	Dose Level ($\mu\text{g}/\text{kg}$)			
		1 (120)	2 (240)	3 (360)	4 (540)
1	MTD = Dose 4	0.05	0.05	0.05	0.05
2	MTD = Dose 4	0.05	0.05	0.07	0.10
3	MTD = Dose 3	0.05	0.07	0.10	0.15
4	MTD = Dose 2	0.05	0.10	0.15	0.20
5	MTD = Dose 1	0.10	0.15	0.20	0.25
6	No MTD	0.15	0.20	0.25	0.30

The scenarios describe the full range of possibilities:

- Scenario 1 considers the case where all doses are safe (i.e., true toxicity probability is below the target threshold for each dose).

- Scenarios 2-5 consider the case where the true target toxicity level of 10% occurs at each successive dose level under consideration.
- Scenario 6 considers the case where no dose level is safe (i.e., true toxicity probability is above the target threshold for all doses).

The results of the simulation study are summarized in Table 5, and contrasted to the results from a pure 3+3 design (which was proposed in the original version of the protocol). Below, we provide a short summary of the findings from the simulation study:

- In scenario 1, both CRM approaches and the 3+3 method select the highest dose with high probability.
- In scenarios 2-5, both CRM approaches generally does a better job at selecting the “correct” dose as the MTD. The 3+3 method does slightly better at selecting the highest dose when it is the MTD (scenario 2). However, this comes at a cost of “overshooting” the MTD when the true MTD occurs at a lower dose – as high as 88% under scenario 5.
- In scenario 6, the CRM approaches correctly conclude that no dose satisfies the criteria of an MTD over half of the time, whereas the 3+3 has a small probability of declaring no MTD and seems to select any of the four doses in a near uniform manner.

Table 5. Results of Simulation Study

Scenario	Dose Level	% Recommended			# Subjects Allocated			% True Toxicity CRM
		CRM	CRM _{lag}	3+3	CRM	CRM _{lag}	3+3	
1	None	0%	1%	1%				
	120	2%	2%	2%	8.1	11.5	3.5	5%
	240	3%	4%	2%	5.3	8.9	3.4	5%
	360	4%	5%	3%	5.4	8.0	3.6	5%
	540	91%	88%	91%	42.2	32.6	45.2	5%
2	None	1%	1%	1%				
	120	4%	4%	2%	9.3	12.4	3.4	5%
	240	9%	9%	2%	8.3	10.8	3.4	5%
	360	19%	19%	10%	10.4	11.4	4.4	7%
	540	68%	67%	86%	36.8	29.7	33.8	10%
3	None	1%	1%	1%				
	120	10%	10%	2%	13.8	15.7	3.5	5%
	240	25%	25%	4%	14.0	14.9	3.6	7%
	360	32%	31%	19%	14.2	13.9	5.0	10%
	540	32%	33%	74%	23.6	20.9	23.1	15%
4	None	1%	2%	1%				
	120	27%	26%	2%	22.0	22.5	3.5	5%
	240	42%	42%	8%	19.1	19.3	4.1	10%
	360	21%	21%	29%	12.4	12.6	5.6	15%
	540	9%	10%	59%	12.1	11.1	15.5	20%
5	None	21%	20%	3%				
	120	54%	54%	9%	37.4	36.9	4.0	10%
	240	20%	20%	16%	12.5	13.9	4.4	15%
	360	5%	5%	32%	6.1	6.4	5.2	20%
	540	1%	1%	41%	4.8	3.8	9.4	25%
6	None	61%	61%	6%				
	120	34%	34%	19%	39.4	39.0	4.5	15%
	240	4%	4%	22%	6.2	7.7	4.5	20%
	360	1%	1%	29%	2.8	2.7	4.4	25%
	540	0%	0%	24%	1.9	1.3	5.2	30%

In summary, both the modified CRM and lagged CRM approaches generally have better performance than the 3+3 design with respect to successfully recommending the correct dose as the MTD (based on prior assumptions), and either would be well suited to achieve the goals of this study. The modified CRM design

being used here performs better than the more traditional approach at identifying the true MTD when it occurs at one of the intermediate doses. Clearly, better accuracy could be achieved by increasing the sample size for the study. However, when weighted against the costs of a larger study, the proposed sample size provides the right balance with respect to selecting the correct dose across all scenarios, and considering the probabilities of both “undershooting” and “overshooting” the assumed true MTD. Some efficiency is sacrificed by using the lagged version of the modified CRM. However, this minor loss of efficiency is completely offset by the operational advantages of requiring fewer “extra placebo subjects” to be enrolled.

